### **5.6.3 Withdrawal of informed consent**

Subjects may voluntarily withdraw consent to participate in the study for any reason at any time. Withdrawal of consent from the study is defined as when a subject:

- Does not want to participate in the study anymore  
and
- Does not want any further visits or assessments  
and
- Does not want any further study related contacts  
and
- Does not allow analysis of already obtained biologic material

In this situation, the investigator must make every effort (e.g. telephone, e-mail, letter) to determine the primary reason for the subject's decision to withdraw his/her consent and record this information.

Study treatment must be discontinued and no further assessments conducted, and the data that would have been collected at subsequent visits will be considered missing.

Further attempts to contact the patient are not allowed unless safety findings require communicating or follow-up.

All efforts should be made to complete the assessments prior to study withdrawal. A final evaluation at the time of the patient's study withdrawal should be made as detailed in the assessment table below.

#### **5.6.4 Loss to follow-up**

For subjects whose status is unclear because they fail to appear for study visits without stating an intention to discontinue or withdraw, the investigator should show "due diligence" by documenting in the source documents steps taken to contact the subject, e.g. dates of telephone calls, registered letters, etc. A subject cannot be considered as lost to follow-up until the time point of his/her scheduled end of study visit has passed.

#### **5.6.5 Early study termination by the sponsor**

The study can be terminated by Novartis at any time for any reason. This may include reasons related to the benefit risk assessment of participating in the study, practical reasons, or for regulatory or medical reasons (including slow enrolment). Should this be necessary, the subject must be seen as soon as possible and treated as a prematurely withdrawn subject. The investigator may be informed of additional procedures to be followed in order to ensure that adequate consideration is given to the protection of the subject's interests. The investigator will be responsible for informing the Institutional Review Board/Independent Ethics Committee (IRBs/IECs) of the early termination of the trial.

### **6 Visit schedule and assessments**

All assessments are listed in [Table 6-1](#). Assessments that are to be reported in the clinical database are marked with an 'X'. Assessments that will only be reported in the source documentation are marked with an 'S'. Subjects should be seen for all visits on the designated day or as close to it as possible, with an allowed visit window of  $\pm$  3 days for visits 1, 3, 5, 6, 8, 10, 11, and 13.. Study staff should call subjects for all tele-visits on the designated day or as close to it as possible, with an allowed visit window of  $\pm$  3 day for visits 2, 4, 7, 9 and 12.

Eligible subjects may start study treatment once it is confirmed that they meet all inclusion criteria and none of the exclusion criteria.

[figure not shown]
Subjects may be contacted for safety evaluations for 30 days after the last dose. Documentation of attempts to contact the subject should be recorded in the source documentation. Unscheduled visits for safety/medication evaluation/unscheduled assessments are permitted at any time during the study.

**Table 6-1** **Assessment schedule**

Phase	Screening/Baseline		Randomized Treatment						Open Label Extension				Unscheduled ◊	
Visit Number	1	2	3	4	5	6	7	8	9	10	11	12	13/EOS	
Days	- Day 14	- Day 7 to - Day 1	Day 1	Day 7	Day 14	Day 28	Day 42	Day 56	Day 63	Day 70	Day 84	Day 98	Day 112	UNSCHED
Time of Visit	Week -2	Week -1	Day 1	Week 1	Week 2	Week 4	Week 6	Week 8	Week 9	Week 10	Week 12	Week 14	Week 16	UNSCHED
Visit type	Office	Tele-visit	Office (randomization)	Tele-visit	Office	Office	Tele-visit	Office	Tele-visit	Office	Office	Tele-visit	Office	Office
Titration					X	X		X		X	X			
Laboratory Evaluations (per protocol) 	X		X		X			X		X			X	X
Urine pregnancy (site) 	X													
Serum pregnancy			X			X		X			X		X	
Open label titration for control arm								X (control only)						
Randomization			X											
Sensor use training 	S													
ActiWatch Exchange & Data Upload			X			X		X			X		X	

Phase	Screening/Baseline		Randomized Treatment						Open Label Extension				Unscheduled ◊	
Visit Number	1	2	3	4	5	6	7	8	9	10	11	12	13/EOS	
Days	- Day 14	- Day 7 to - Day 1	Day 1	Day 7	Day 14	Day 28	Day 42	Day 56	Day 63	Day 70	Day 84	Day 98	Day 112	UNSCHED
Time of Visit	Week -2	Week -1	Day 1	Week 1	Week 2	Week 4	Week 6	Week 8	Week 9	Week 10	Week 12	Week 14	Week 16	UNSCHED
Visit type	Office	Tele-visit	Office (randomization)	Tele-visit	Office	Office	Tele-visit	Office	Tele-visit	Office	Office	Tele-visit	Office	Office
Adverse Events/Serious Adverse Events §	X	X §	X	X §	X	X	X §	X	X §	X	X	X §	X	X
Concomitant Medications	X	X	X	X	X	X	X	X	X	X	X	X	X	X
Dosage Administration Record			X		X	X		X		X	X		X	X
Drug Accountability					S	S		S		S	S		S	S
IRT Call	X		X		X	X		X		X	X		X	X
Study Completion/Early Termination													X	
Angioedema Assessments	X		X		X	X		X		X	X		X	X

\*\*IC must be obtained prior to all study specific screening procedures during or as close to the start of the screening phase as possible  
 ◊ = Unscheduled visit assessments marked with (X) are optional procedures that may be performed at the investigators discretion, or if the patient withdraws early from treatment or study.  
 X = assessment to be recorded on clinical data base  
 S = assessment to be documented in source data  
 1. Height should be measured in centimeters if possible  
 2. Weight should be captured in every office visit to the nearest 0.1 kg, without shoes and in indoor clothing  
 3. Laboratory evaluations include Chemistry, Hematology, and Urinalysis  
 4. Urine pregnancy test must be performed on site at visit 1  
 5. [REDACTED]  
 6. Activwatch to be provided at baseline visit.  
 7. [REDACTED]  
 8. At visit 2, 4, 7, 9, and 12 if a subject reports an angioedema-like event, the subject should be requested to come in for an unscheduled visit for safety assessment.

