**Table 5-4 Treatment Dose Levels during the open-label epoch**

Dose Level*	Sacubitril/valsartan
1	24/26 mg BID
2	49/51 mg BID
3	97/103 mg BID

\*sacubitril/valsartan 24/26 mg BID (Dose Level 1) will be given to subjects who completed the double-blind treatment epoch on Dose Level 1 and is also available if down-titration is required.

Open-label sacubitril/valsartan will be packaged and labeled by the sponsor in accordance with the US Code of Federal Regulation governing handling of investigational treatments, and will be dispensed by the study physician. Open-label treatment will be provided for 8 weeks.

All subjects entering the open label-treatment epoch will be given sacubitril/valsartan 49/51 mg BID (Dose Level 2) unless they completed the double-blind treatment epoch on Dose Level 1. Instead, these subjects will enter the open-label epoch on sacubitril/valsartan 24/26 mg BID dose (Dose Level 1). At each subsequent study visit during the open-label epoch, the study physician will sequentially up-titrate the study drug dose (based on clinical tolerance and the USPI) to achieve the targeted desired dose of 97/103 mg sacubitril/valsartan BID (Dose Level 3).

During the open label phase, patients not tolerating the escalation from Dose Level 1 to Dose Level 2 (or Dose Level 2 to Dose Level 3) can be titrated down to the next lower Dose Level, if, in the investigator's judgement, the adjustment/elimination of concomitant medications is not possible or does not alleviate the side effects of concern. See [Section 5.5.5](#).

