### **5.4 Treatment blinding**

Subjects, investigator staff, persons performing the assessments, data analysts and the Clinical Trial Team (CTT) will remain blind to the identity of the treatment from the time of randomization until database lock, using the following methods: (1) Randomization data are kept strictly confidential until the time of unblinding, and will not be accessible by anyone else involved in the study with the exception of the IRT provider generating the randomization code. (2) The identity of the treatments will be concealed by the use of investigational treatments that are identical in packaging, labeling, and schedule of administration, appearance, taste and odor.

A double-dummy design is used because the identity of the study drug cannot be disguised, as the drug products are visibly different. To maintain the blinding, subjects will be required to take their assigned active treatment tablet along with placebo matching the opposite treatment twice daily.

Unblinding will only occur in the case of subject emergencies (see [Section 5.6](#)) and at the conclusion of the study.

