- All subjects that complete the 8 week double-blind treatment epoch will proceed into the 8-week open-label epoch on sacubitriI/valsartan.
- At Week 8 (Visit 8), Drug accountability will be performed and all double-blind treatment medication will be returned to the site.

- Open-label sacubitril/valsartan will be dispensed at Week 8 (Visit 8) with subject's instructions **NOT** to start their open label-treatment until after completing a 36-hour wash out. All patients will have the wash out in order to maintain the blinding of the core study.

All dose levels will be available throughout the study. Dose adjustments to lower dose levels may be made at any time at both scheduled and unscheduled visits only if indicated for blood pressure control/tolerability reasons.

All study treatment assigned by the IRT will be recorded/databased in the IRT.

All dosages prescribed and dispensed to the subject and all dose changes during the study must be recorded in the IRT and on the Dosage Administration Record eCRF.

Study medication should be taken twice daily with a glass of water with or without food.

If the subject misses taking any study drug dose, he/she should take it as soon as possible and within 4 hours of the scheduled dose time. If the patient is unable to take the missed dose within 4 hours of the scheduled dose time, he/she should skip the missed dose and return back to his/her regular study drug administration schedule.

The investigator must promote compliance by instructing the subject to take the study treatment exactly as prescribed and by stating that compliance is necessary for the subject's safety and the validity of the study. The subject must also be instructed to contact the investigator if he/she is unable for any reason to take the study treatment as prescribed.

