## **8.3 Database management and quality control**

CRO working on behalf of Novartis review the data entered into the CRFs by investigational staff for completeness and accuracy and instruct the site personnel to make any required corrections or additions. Queries are sent to the investigational site using an electronic data query. Designated investigator site staff is required to respond to the query and confirm or correct the data.

Concomitant medications entered into the database will be coded using the WHO Drug Reference List, which employs the Anatomical Therapeutic Chemical classification system. Concomitant procedures, non-drug therapies and adverse events will be coded using the Medical dictionary for regulatory activities (MedDRA) terminology.

Laboratory samples will be processed centrally and the results will be sent electronically to Novartis (or a designated CRO).

Diary data will be entered into an electronic diary by the subject who will fill in their PRO data in a site based tablet. The system will be supplied by a vendor(s), who will also manage the database. The database will be sent electronically to Novartis personnel (or designated CRO).

Randomization codes and data about all study drug(s) dispensed to the patient and all dosage changes will be tracked using an Interactive Response Technology (IRT). The system will be

supplied by a vendor, who will also manage the database. The database will be sent electronically to Novartis (or a designated CRO).

Each occurrence of a code break via IRT will be reported to the clinical team and monitor. The code break functionality will remain available until study shut down or upon request of Novartis.

The occurrence of relevant protocol deviations will be determined. After these actions have been completed and the database has been declared to be complete and accurate, it will be locked and the treatment codes will be unblinded and made available for data analysis. Any changes to the database after that time can only be made after written agreement by Novartis management.

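### Table 6-1 lists a Visit 8 open-label titration for the control arm only, which conflicts with the blind to database lock and with the arm-neutral open-label entry rule

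*Protocol*

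**What the plan says.** The schedule of assessments (Protocol Table 6-1) contains a row named "Open label titration for control arm". Its only entry is in the Visit 8 column and reads "X (control only" followed by a closing bracket. The legend states "X = assessment to be recorded on clinical data base". A separate, general titration row in the same table is also marked at Visit 8, with no restriction by arm.

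Protocol Section 5.4 says that patients, site staff, assessors, data analysts and the trial team "will remain blind to the identity of the treatment from the time of randomization until database lock". It adds "Unblinding will only occur in the case of subject emergencies" and at the end of the study. Section 8.3 puts release of the codes after the database is declared complete: "it will be locked and the treatment codes will be unblinded and made available for data analysis".

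Protocol Section 5.1.1 gives the rule for entering the open-label phase: "All subjects entering the open label-treatment epoch will be given sacubitril/valsartan 49/51 mg BID (Dose Level 2) unless they completed" the double-blind phase on Dose Level 1. Section 5.5.4 and SAP 1.1 repeat the rule. On the second washout, Section 5.5.4 says "All patients will have the wash out in order to maintain the blinding of the core study", and SAP 1.1 gives the same reason alongside angioedema risk.

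**The concern.** The text describes a move into open-label treatment that a site can manage without knowing which drug the patient had been taking. The table adds a step at the same visit that applies to one arm only. To decide whether the step applies to a given patient, the site needs the assignment, which Section 5.4 withholds from it until lock.

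If the row were put into effect in some way, for example through a distinct action or a form field completed only for control patients, its presence or absence would identify the arm. This could happen about eight weeks before the patient's last visit, while data are still being collected, queried and classified. It would also undo the purpose of washing out both arms at Week 8.

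**Working it through.** No power, sample-size or error-rate calculation bears on this point. The check is of position, consistency and consequence.

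**1. Is the mark really at Visit 8?** The entry lies in the eighth visit column. The laboratory row of the same table, counted in the same way, falls at Visits 1, 3, 5, 8, 10 and 13, which is what Sections 6.5.5.1 to 6.5.5.3 list. The general titration row falls at Visits 5, 6, 8, 10 and 11 (Weeks 2, 4, 8, 10 and 12), which agrees with Section 3.6. The column positions can therefore be trusted, and the control-only mark is at Visit 8, Day 56.

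**2. Is it a second label for the general titration step?** The table does not say so. The general row already covers Visit 8 for everyone, and the control-only row stands apart from it with its own restriction.

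**3. Set against the other provisions:**

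| Provision | Depends on arm? | Compatible with the row? |
|---|---|---|
| Blind to database lock (Protocol 5.4) | No; binds all site and trial staff | No |
| Permitted unblinding (Protocol 5.4) | Emergencies and end of study; open-label entry not listed | No |
| Code release after lock (Protocol 8.3) | No | No |
| Open-label entry rule (Protocol 5.1.1, 5.5.4; SAP 1.1) | No; depends on dose level completed | No |
| Week 8 washout (Protocol 5.5.4; SAP 1.1) | No; all patients, to keep the blind | The row defeats its stated purpose |
| Pack assignment by IRT (Protocol 5.1.1) | Not stated for open-label packs | No concealed control-only step is described |

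**4. How many patients?** Section 9.8 plans for 136 randomized and 20% drop-out. If all of that drop-out came before Visit 8, 136 × 0.8 = 108.8, or about 109, would reach it. That counts patients who arrive at the visit where the row applies. It does not estimate how many would be unblinded, and the documents give no basis for such an estimate.

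**5. Which data could be affected?**

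- *Week 8 actigraphy (primary).* It is essentially recorded by Visit 8, when the device is exchanged and uploaded. Section 6.6.4 has the vendor score it blinded to treatment. The direct exposure is small.
- *Site-assessed data.* NYHA class and signs and symptoms are assessed at Visit 8 and at later office visits (Section 6.5.1). Adverse events are followed at each visit for changes in severity and suspected relationship (Section 7.1). An event that began in the double-blind phase can therefore still be re-rated after Visit 8.
- *Decisions before lock.* Section 8.3 places data queries and the determination of protocol deviations before lock. A database field filled for control patients only would be visible to staff handling that work.
- *Weeks 9 and 16.* All patients are then on known open-label drug, and Section 9.5.1 and SAP 2.7.2 use paired tests within each randomized group. There is no blinded comparison between arms at these times to protect.

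**The case against.** The best defence is that the row cannot be acted on. Only the IRT provider holds the randomization data, IRT assigns packs at every visit, and a code break requires the investigator to confirm that it is necessary. A blinded site meeting this row would probably raise a query or leave the field empty. The row may be no more than a label for the point at which enalapril patients first receive sacubitril/valsartan. Most of this stands: sites that follow Sections 5.1.1 and 5.5.4 remain blind, and the documents show no site actually learning the arm. It does not rescue the row. Section 6 says that all assessments are listed in Table 6-1, so sites will consult it, and the harmless readings are inferences that no text confirms.

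IRT could in theory direct an arm-dependent step without naming the arm. No such mechanism is described, and a step given to one arm only would itself reveal the arm.

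Three stronger readings are tempting but unsupported. A reader might infer that about 109 patients would be unblinded; that figure is only the number expected to reach Visit 8 under one assumption about when drop-out occurs. A reader might infer that the primary endpoint is compromised; the timing of recording and the blinded vendor scoring argue against it. A reader might also infer that the table is wrong and the text right; the documents show only that they disagree.

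On safety, it is fair to add that the randomized phase closes at the Week 8 visit (SAP 2.1.1) and that no inferential safety analysis is planned (SAP 2.8). This limits the harm from re-rated events but does not remove it.

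**Conclusion.** The inconsistency is real, and the row is wrong as written in the sense that blinded staff cannot perform or record it. Putting it into effect would disclose assignment before lock, contrary to Section 5.4. It is a conflict between the schedule and the text. It does not show that the sponsor intended an arm-specific step.

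Its size cannot be stated as a number of patients. It ranges from none, if every site follows the text, up to all who reach Visit 8 if the row is implemented throughout. The consequence is moderate: possible bias in site-assessed data at and after Visit 8, in the later rating of double-blind adverse events, and in query and deviation handling before lock. The conclusion that the primary measurement faces little direct threat rests on the Week 8 recording being essentially complete at Visit 8 and on vendor scoring staying blinded as stated. The point deserves correction because a break of the blind cannot be repaired afterwards and the correction is cheap.

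**What to change.** Reconcile Table 6-1 with Protocol Sections 5.1.1, 5.4 and 5.5.4 and SAP 1.1, so that no Visit 8 procedure and no database field discloses treatment assignment to anyone who must remain blind. Which titration rule applies at open-label entry is for the sponsor's clinical team, and this point takes no position on it. Check at the same time that the case report form holds no field corresponding to the row that would be completed for one arm only.

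The cost is one table row, changed by amendment or site clarification letter, plus the form check. Sample size and the planned analyses are unaffected. If patients have already passed Visit 8, ask sites how they handled the row and record any resulting unblinding. The SAP's disposition summary (2.3.1) lists unblinding by site only under premature discontinuation in the double-blind phase, so it would not show a patient who completed that phase and was unblinded at Visit 8.

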## **6.1 Information to be collected on screening failures**

All subjects who have signed informed consent but not entered into the next epoch will have the study completion page for the screening epoch, demographics, inclusion/exclusion, and serious adverse event (SAE) data collected. Adverse events that are not SAEs will be followed by the investigator and collected only in the source data.

## **6.2 Patient demographics/other baseline characteristics**

Subject demographic and baseline characteristic data to be collected on all subjects include: year of birth, age, sex, race, ethnicity, relevant medical history/current medical condition present before signing informed consent where possible, diagnoses and not symptoms will be recorded. HF medications and other CV medications will be recorded in eCRFs such that they can be separated from other medications. Likewise, detailed HF history and other relevant CV medical history will be recorded on eCRFs separately from other medical history.

Investigators will have the discretion to record abnormal test findings on the Medical History eCRF whenever in their judgment, the test abnormality occurred prior to the informed consent signature.

## **6.3 Treatment exposure and compliance**

Compliance will be assessed by the investigator and/or study personnel at each visit using pill counts and information provided by the care giver. This information should be captured in the source document at each visit.

Subject compliance should be at least 80% during the titration and maintenance treatment phase. The investigator and/or study personnel will counsel the subject if compliance is below 80%. Study drug accountability will also be determined by the site monitor while performing routine site visits and at the completion of the study.

Duration of the study titration and maintenance study drug exposure will be calculated based upon the start and stop dates recorded in the eCRF.

## **6.4 Efficacy**

### **6.4.1 Efficacy assessment**

The efficacy end points are:

#### **Primary:**

The change in mean activity counts collected during the most active 30 minutes of the subject's day between baseline phase (mean of data collected each day during week -1) and the final randomized treatment phase (mean of data collected each day during week 8), as measured by wrist-worn accelerometer collected actigraphy (total counts per 30 min period collected during the most active 30 minutes of each day).

